The EYE Check Tonometer satisfies all the above-mentioned criteria necessary for practical large-scale implementation of home IOP monitoring. The instrument comprises of an optical head, a flexible arm and a power and control unit. The optical head is similar to the Goldmann tonometer. It is composed of an acrylic transparent probe connected internally to a force sensor and an optical monitor which monitors the contact of the probe with the cornea. In addition, it contains a light pattern for self-alignment.

In operation, the subjects, seated in front of a table on which the device is placed, move their head to center the visible pattern in the optical head by adjusting the flexible arm. An audible message informs them when their eye is aligned with the optical head. Upon confirmation of adequate centering, the subjects bring the cornea in contact with the probe by leaning towards the probe. The probe moves and activates the force sensor while the area of contact is recorded. When a preset safe pressure is registered, an audible signal informs the subject to lean back and the fixation light is turned off. The output of the force sensor and the optical monitor are sampled frequently and transmitted to a laptop computer (to be replaced by a smartphone in the future). Following the procedure, the IOP is derived and quality control assessments are performed.

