## Design & Procedures

Prospective consecutive series of 50 adult patients. Consecutive patients coming to the Duke Eye Center will be approached by a research coordinator for the possibility of participating in the study. Subjects will be screened based on the inclusion and exclusion criteria (Selection of Subjects section). Eligible and willing patients will be asked to sign the consent form for the study.

Participants will be assigned a unique code number. The key to this code will be in a locked key file with the principal investigator. Both eyes will be evaluated in this study. The user (patient) will then be informed by a skilled technician, who is experienced with use of the Eye Check tonometer, on how to use it by themselves.

The subject will perform a self-alignment procedure that trains for alignment and assesses the results. During this procedure, no contact will be made with the probe. The progress will be monitored and recorded. Only subjects who pass the alignment criteria will proceed to obtain IOP measurements. Prior to the instillation of any eye drops, five immediately consecutive readings will be obtained with the Eye Check tonometer. Each of these readings will be recorded in the Eye Check tonometer connected computer without any subject identifier other than the identification code. IOP measurements by a certified ophthalmic technician using the Goldmann Applanation tonometer, within 5 minutes after the use of the Eye Check tonometer will be performed. Other data such as age, pachymetry, refractive error, etc., will be recorded.

Patients will be provided with a questionnaire to assess comfort and ease of use.

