#### Data Analysis & Statistical Considerations

The IOP readings from the Eye Check tonometer and the Goldmann will be compared. The Goldmann measurements are typically considered the gold standard. Mean IOP and standard deviation of IOP measurements using the two devices will be assessed.

If needed, for correlation analyses, data such as age, pachymetry, refractive error, etc., will be obtained by the clinical investigators from the charts.

The data of the Eye Check tonometer, which, as mentioned above, does not contain any subject identification or IOP data, will be analyzed. The IOP, Standard of Measurement, number of successful readings, and performance scores will be derived.

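### No planned analysis shows how far Eye Check and Goldmann differ in the same eye, or whether that difference varies with user performance among the patients who passed alignment and were measured

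*Combined protocol and SAP*

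**What the plan says.** The design is a "Prospective consecutive series of 50 adult patients", and "Both eyes will be evaluated in this study" (Design & Procedures). Each patient first does a no-contact alignment exercise, of which the protocol says "The progress will be monitored and recorded". Then "Only subjects who pass the alignment criteria will proceed to obtain IOP measurements". For those who pass, "five immediately consecutive readings will be obtained with the Eye Check tonometer", and a technician takes the Goldmann reading within 5 minutes. Device readings are stored "without any subject identifier other than the identification code".

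On the device itself, Background & Significance says: "Following the procedure, the IOP is derived and quality control assessments are performed".

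Data Analysis & Statistical Considerations says that the readings of the two devices will be compared, and the summaries it names are the mean and SD for each device. Correlation analyses are optional, and the examples are age, pachymetry and refractive error taken from the charts. On the device data it says: "The IOP, Standard of Measurement, number of successful readings, and performance scores will be derived". No section defines the performance score or assigns it to an analysis.

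**The concern.** The stated purpose is to learn whether Eye Check readings are comparable with Goldmann readings. That is a question about the two values in the same eye, and separate device summaries do not answer it. Two devices can have the same mean and SD and still disagree widely eye by eye.

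The second gap follows from the first. The patient operates Eye Check and a technician operates Goldmann, so user performance is a plausible source of error in one device only. The protocol treats it as such: it trains and assesses alignment, measures only those who pass, and applies quality control. Yet nothing planned asks whether, among measured patients, weaker performance goes with a larger difference from Goldmann. A pooled result could look acceptable while weaker performers get poorer readings. The aim is eventual home use. Here a Goldmann value taken within minutes is available as a check.

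**Working it through.** The plan gives no SD, margin, power or sample-size formula, so it has no figure of its own to reproduce. From the documents: 50 patients, both eyes, five Eye Check readings, Goldmann within 5 minutes, only passers measured. Everything else below is an assumption.

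**1. Device means and SDs do not determine agreement.** If both devices have SD S and same-eye correlation r, the SD of the difference is S × √(2(1 − r)).
- r = 0.9: √0.2 = 0.45, so the limits are ±1.96 × 0.45 S = ±0.88 S.
- r = 0.5: √1.0 = 1.00, so the limits are ±1.96 S.

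The reported means and SDs would be identical in both cases. The two values of r are illustrative.

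**2. What pooling could hide.** Assume that the difference d has mean zero and SD 1.5 mmHg in three quarters of measured eyes, and SD s in the lowest-scoring quarter.
- Pooled SD = √(0.25 s² + 0.75 × 1.5²); limits = ±1.96 × SD.
- The share of eyes with |d| > 5 mmHg is the two-sided normal tail. The pooled share is 0.25 × the low-scorer tail + 0.75 × 0.09% (the tail for SD 1.5).

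| s (mmHg) | Pooled SD | Pooled limits | Low-scorer limits | \|d\| > 5, pooled | \|d\| > 5, low scorers |
|---|---|---|---|---|---|
| 2.25 | 1.72 | ±3.4 | ±4.4 | 0.7% | 2.6% |
| 3 | 1.98 | ±3.9 | ±5.9 | 2.5% | 9.6% |
| 4 | 2.38 | ±4.7 | ±7.8 | 5.4% | 21% |

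**3. What the extra analysis could detect.** Simulation with 6,000 runs per cell: two eyes per patient, within-patient correlation 0.5, uniform score that identifies the high-error quarter perfectly, Spearman test of score against the patient's mean |d|, two-sided 5%.

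| Patients measured | s = 2.25 | s = 3 | s = 4 | No dependence |
|---|---|---|---|---|
| 50 | 29% | 59% | 82% | 5% |
| 40 | 23% | 50% | 72% | 5% |
| 30 | 18% | 39% | 59% | 5% |

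A score that identifies those eyes imperfectly would give less power.

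In terms of a plain correlation, with one value per patient, the smallest r detectable with 80% power is tanh((1.96 + 0.84)/√(n − 3)): 0.39 for n = 50, 0.43 for n = 40, 0.49 for n = 30.

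**4. Effect of measuring only passers.** Suppose that the score measures what the alignment step selects on, is normal, and is cut off from below. A correlation of 0.40 in all patients then shrinks among passers:
- none fail: 0.40, n = 50, power about 83%;
- 20% fail: about 0.32, n = 40, power about 51%;
- 40% fail: about 0.27, n = 30, power about 31%.

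**5. Precision by score group.** A third of 50 patients is about 16. Counting each patient as one observation, the 95% confidence interval for an SD runs from √(15/27.49) = 0.74 to √(15/6.26) = 1.55 times the estimate.

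**The case against.** The strongest reply is that nothing is lost. Alignment progress, device readings and Goldmann readings are all recorded and can be joined by the identification code, so the analysis can be run at any time. The list of correlation variables is also open-ended. The first part stands: a reader might infer that the trial cannot show whether agreement depends on performance, but the documents support only that no analysis is planned to show it. The second part helps less, because the open-ended list concerns chart data, performance scores come from the device, and the sentence names no outcome.

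A reader might also infer that the omission is what prevents the trial from showing whether the alignment requirement protects accuracy. That does not follow. Patients who fail alignment have no Eye Check reading, so no analysis of measured patients can show what the requirement excludes. This is a limit of the design, and the fix leaves it in place.

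A reader might further take the performance score to be alignment quality. The documents do not say so. It could reflect contact quality, reading success or training progress.

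Finally, the score analysis is a secondary refinement with modest power, and any rule that changes the report when the spread looks wider at low scores could be set off by chance. Both points stand. They are reasons to put the overall paired analysis first, label the score analysis exploratory and use no trigger. They are not reasons to leave it out.

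**Conclusion.** The point holds in limited form. As written, the plan yields neither a same-eye measure of agreement nor any check of whether agreement varies with user performance among patients who passed and were measured. The first gap is the more basic one, because the score analysis needs the paired difference as its outcome.

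Under the assumed SDs, pooled limits could understate the low scorers' limits by about 1 mmHg (4.4 − 3.4) to about 3 mmHg (7.8 − 4.7) on each side. These figures rest on an assumed one-quarter share and assumed SDs; the documents neither support nor exclude them. With at most 50 patients the score analysis would reliably detect only strong dependence. This is an inexpensive improvement to the analysis plan. It does not show that the data are inadequate for comparing the devices.

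**What to change.** Amend Data Analysis & Statistical Considerations to say the following.

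1. The performance score is defined: what it measures, at which step, and whether per reading, eye or patient.
2. For each measured eye, d = Eye Check minus Goldmann is computed, with a stated rule for reducing the five Eye Check readings to one value.
3. The overall mean difference and 95% limits of agreement are reported with confidence intervals, with the patient as the cluster.
4. As a pre-specified exploratory analysis, d and |d| are related to the continuous score by a clustered regression or rank correlation. Limits of agreement by score are shown descriptively, whatever the result.
5. The number of patients who failed alignment is reported. Inference is limited to those who passed, and the analysis cannot show whether the alignment requirement itself protects accuracy. With at most 50 patients, a null result is not evidence of no dependence.

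The cost is one paragraph and a little extra analysis of data already to be collected, with no new patients, visits or procedures. The downside is imprecision: limits for about 16 patients in a lowest third would be wide, which is why they should be descriptive only.

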#### Data & Safety Monitoring

Patients will be advised to report any adverse event immediately to the principal investigator.

The investigating physicians will document and report the adverse events. A high rate of adverse reactions will prompt the termination of the study.

Adverse events could include corneal abrasions, corneal, or conjunctival infections if the probe is not handled in an aseptic fashion by the patient or caregiver. Thus, the patient would be asked to call if there was any redness of the eye, any discharge, excessive watering, blurry vision, or eye pain.

Reportable adverse events will be submitted to the DUHS IRB per policy.

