### Subject Recruitment

Patients will be recruited from the glaucoma clinic who are already scheduled for a standard of care visit. Someone known to them will introduce the study to them and if interested a member of the study team will review the study and obtain consent before any study procedures are done. Approximately 50 subjects will be enrolled in this study.

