### Risk/Benefit Assessment

Risks: It is possible that the patient may abrade the cornea during a measurement resulting in a corneal abrasion. The likelihood of such an event occurring with the Eye Check tonometer is remote due to the disposable probe cover made out of contact lens material (thus protecting the cornea) during the measurement. Pain, redness, watering, and blurry vision are symptoms that would alert the patient immediately and they will be instructed to contact the principal investigator and stop the study. Such abrasions typically heal within 24-48 hours unless the patient is a diabetic in whom it may take longer and thus a history of diabetes is an exclusion factor. There is a remote possibility that the corneal abrasion can get infected.

Sanitation of device - The head of the unit will be bent so that the entire tip will be dipped in the standard cleaning solutions (those used for Goldmann tonometer tips), then dried (per the current

protocol), and then used on any subsequent patient in the study. The actual device will be wiped down with cavi wipe per standard clinic protocols.

Benefits: The physician will be able to assess the accuracy of the IOP measurements with the Eye Check tonometer, which has the potential to be used as a device by which the patients can check their own IOP at home in the future. This may lead to better management of their glaucoma.

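### Termination rests on a rate of adverse reactions, but after the visit events are found only if the patient reports them

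*Combined protocol and SAP*

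**What the plan says.** The only study-level safety rule is in Data & Safety Monitoring: "A high rate of adverse reactions will prompt the termination of the study". The section gives no figure for a high rate, no denominator, no time of review and no decision maker.

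The same section describes how events come to light. "Patients will be advised to report any adverse event immediately to the principal investigator". For later symptoms, "the patient would be asked to call if there was any redness of the eye", and likewise for discharge, excessive watering, blurry vision or eye pain. On recording, "The investigating physicians will document and report the adverse events".

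Risk/Benefit Assessment takes the same approach. It describes pain, redness, watering and blurry vision as "symptoms that would alert the patient immediately and they will be instructed to contact the principal investigator". It adds: "Such abrasions typically heal within 24-48 hours unless the patient is a diabetic in whom it may take longer". Infection of an abrasion is named there as a remote possibility, and Data & Safety Monitoring lists corneal and conjunctival infection among the possible events.

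On scale, Subject Recruitment says "Approximately 50 subjects will be enrolled in this study", from patients already booked for a standard-of-care visit. Design & Procedures says "Both eyes will be evaluated in this study". That section ends with a questionnaire on comfort and ease of use, which is not described as adverse-event collection.

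**The concern.** To act on a rate, the study must know who had an event among all who were exposed, over a common period. For the time after the visit, the plan describes a passive method only, and such a method can miss events. On the protocol's own account an abrasion usually heals within one to two days, so a patient could have one, recover and never call. Infection, the other named harm, would be expected to show itself after the visit. In neither case does silence tell the investigators that nothing happened.

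What is at stake is the termination rule. Patients are enrolled consecutively, so later participants may be exposed while earlier events remain unreported. If the recorded rate is too low, the rule is less likely to act when it should.

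**Working it through.** **No figure to reproduce.** The documents give no event rate (only the word *remote*), no reporting rate and no threshold. The check is therefore a reading of the text followed by an illustration on stated assumptions.

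**Routes by which an event can be found**

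| Period | Route described | Active or passive |
|---|---|---|
| During the visit | Patient reports at once; physicians document | Passive; no safety examination is described |
| During the visit | Goldmann reading by a technician within 5 minutes of Eye Check | A contact, but not described as a safety check |
| After the visit | Patient calls or contacts the principal investigator | Passive |
| After the visit | Scheduled call, visit or examination | None described |

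The Goldmann procedure, as described in Background & Significance, includes an anesthetic drop. By inference this could mask early symptoms while the patient is still in clinic.

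**Illustration.** Inputs:
- n = 50 participants (Subject Recruitment).
- p = true event rate per participant: assumed.
- s = share of affected participants whose event is recorded: assumed.

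Participants are treated as independent, and the denominator is taken as all 50. The expected recorded rate is then p × s, and the chance of recording no event is (1 − p·s)^50.

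With p = 4%:

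| s | p·s | Expected recorded events (50·p·s) | Chance of no recorded event |
|---|---|---|---|
| 100% | 4.0% | 2.0 | 0.960^50 = 13% |
| 90% | 3.6% | 1.8 | 0.964^50 = 16% |
| 80% | 3.2% | 1.6 | 0.968^50 = 20% |
| 50% | 2.0% | 1.0 | 0.980^50 = 36% |
| 25% | 1.0% | 0.5 | 0.990^50 = 61% |

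These are chances of an empty record, not of the rule failing, because nothing says how many events make a high rate. To show the effect on a count-based trigger, take p = 10% and an arbitrary count of 5 or more recorded events, used only as an example. The binomial probability of reaching it, P(X ≥ 5) with X ~ Bin(50, p·s), is:

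| s | 100% | 90% | 80% | 70% | 50% |
|---|---|---|---|---|---|
| P(X ≥ 5) | 57% | 47% | 37% | 27% | 10% |

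Finally, suppose no events are recorded in 50 participants. The one-sided 95% upper bound on the recorded rate is 1 − 0.05^(1/50) = 5.8%. Dividing by s gives the bound on the true rate: 5.8% / 0.9 = 6.5% and 5.8% / 0.5 = 11.6%.

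**The case against.** The strongest reply is that the plan is less closed than it may look. A reader might infer that events count only when a patient calls in after the visit. The text does not say so: patients are to report immediately, physicians document events without restriction on source, and a technician sees the patient within minutes of the device being used. Events at the visit can be captured.

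A reader might also infer that patients who do not call are counted as event-free. No sentence says that either. It would be the practical result of dividing by everyone enrolled, but the plan gives no classification rule and no denominator.

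Third, the protocol expects abrasions to cause symptoms that the patient notices at once, and it gives an instruction to report them. That limits under-reporting. At 90% or 80% reporting the chance of an empty record moves only from 13% to 16% or 20%.

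Fourth, the net direction is not certain. Goldmann contact follows Eye Check in the same visit and no attribution rule separates their events, so events due to Goldmann could raise the count.

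Fifth, it is tempting to say that an undercount would undermine a claim of safety for home use. The stated purpose is comparability of pressure readings, and the analysis section plans no safety conclusion. The statement that the device meets the requirements for home use is made in the background, not drawn from this study's event rate.

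All five points narrow the concern. None supplies a way of learning the post-visit outcome of a patient who stays silent.

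**Conclusion.** The concern holds in a limited form. After the visit, the plan relies wholly on the patient to report, while its termination rule depends on a rate. Unreported post-visit events cannot be told apart from no event, and that omission tends to lower the rate. The amount is unknown. It is small if nearly all affected patients report and large if half or fewer do, and the documents do not say which applies. Every percentage in the working rests on assumed event and reporting rates and shows a pattern, not an estimate.

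A second gap compounds the first: *high* has no value and the rate has no unit (patient or eye), so the rule could not be applied consistently even with complete reporting. The point merits a change because the remedy is cheap and the rule is the study's only study-level safety safeguard.

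**What to change.** Amend Data & Safety Monitoring as follows.

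1. Keep the instruction to call, and add one scheduled phone or portal contact by the existing research coordinator with every participant. It should ask about the five symptoms already listed there (redness, discharge, excessive watering, blurry vision, eye pain) as fixed yes/no questions.
2. Let the investigators set the timing so that it covers both abrasion and later infection. A time taken from abrasion healing alone may miss infection.
3. Compute the rate among participants whose outcome is known by any route: the scheduled contact, a patient's own call, or an event documented at the visit. Anyone in the numerator is then also in the denominator. The lack of an event at the visit should not by itself count as a known post-visit outcome.
4. Report the number not reached as unknown rather than event-free, beside the rate. If many are unknown, the rate among the rest may lean upward, because affected patients are the ones likely to call.
5. Have the investigators state what counts as high and whether the unit is the patient or the eye. No value is proposed here.

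The cost is about 50 short contacts and a small amendment. The recorded rate of mild events will probably rise slightly, which the investigators should bear in mind when they define *high*.
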